	
examine the subject to establish the clinical diagnosis of Actinic Keratosis (defined as the presence of 4 to 8 clinically typical, visible, discrete, nonhyperkeratotic, nonhypertrophic Actinic Keratosis lesions) contained within a contiguous 25cm² area on the trunk or extremities (“treatment area”)
 
The number of Actinic Keratosis lesions in the selected treatment area will be counted (and a total provided) and recorded at Visit 1/ Day 1 (Baseline) and at Visit 4/Day 57 (should any exist) on source documentation and eCRFs. Additionally, new lesions not present at the baseline visit will also be counted and recorded on source documentation and eCRFs at Visit 4 or an Unscheduled Visit if applicable.
 
At Visit 4/Day 57, the principal investigator or sub-Investigator will visually inspect the treatment area for any lesions and will confirm complete clearance of Actinic Keratosis lesion in the eCRF if lesion count is equal to zero at Visit 4/Day 57. Complete clearance is defined as the absence of clinically visible Actinic Keratosis lesions identified at Visit 1 or new lesions since Visit 1.
 
At the baseline visit (prior to initial dosing) and each subsequent visit, application site reactions of erythema, flaking/scaling, crusting, swelling, vesiculation/pustulation, and erosion/ulceration will be recorded on the source document and eCRF.

Endpoints:
	
The primary efficacy endpoint will be the proportion of subjects with clinical success defined as complete clearance (absence) of all clinically visible Actinic Keratosis lesions identified at the baseline visit and no new Actinic Keratosis lesions in the treatment area at Visit 4/Day 57.

Safety:
	
The incidence of all adverse events reported during the study will be summarized by treatment group. Equivalence of the test and reference with regard to safety will be evaluated by comparing the nature, severity and frequency of their adverse event profiles. In addition, the test and reference treatments’ frequency and distribution of application site reactions of erythema, flaking/scaling, crusting, swelling, vesiculation/pustulation, and erosion/ulceration will be summarized and compared descriptively.

ABBREVIATIONS

AE	Adverse Event
AK	Actinic Keratosis
ANOVA	Analysis of Variance
ATC	Anatomic Therapeutic Chemical (classification of drugs)
eCRF	Electronic Case Report Form
EDC	Electronic Data Capture
FDA	US Food and Drug Administration
GCP	Good Clinical Practice
ICH	International Conference on Harmonization
IGA	Investigator’s Global Assessment
IRB	Institutional Review Board
ITT	Intent to treat population
IUD	Intra-Uterine Device
LOCF	Last Observation Carried Forward
MedDRA	Medical Dictionary for Regulatory Activities
mITT	Modified Intent To Treat population
OTC	Over the counter
PI	Principal Investigator
PP	Per protocol population
Rx	Prescription
SAE	Serious Adverse Event
SAP	Statistical Analysis Plan
SPF	Sun Protection Factor
Sub-I	Sub-Investigator

1. BACKGROUND

[REDACTED]

[REDACTED]

[REDACTED] Perrigo
New York, Inc. has developed a generic formulation of Ingenol Mebutate Topical Gel 0.05%.

2 STUDY OBJECTIVES

The objectives of this study are to compare the safety and efficacy profiles of Perrigo New York, Inc.'s Ingenol Mebutate Topical Gel 0.05% to Picato® Topical Gel 0.05% (Ingenol Mebutate Topical Gel 0.05%) and to demonstrate the superior efficacy of the two active formulations over that of the vehicle in the treatment of Actinic Keratosis.

2.1 Endpoints

The **primary efficacy endpoint** will be the proportion of subjects with clinical response of success defined as complete clearance (absence) of all clinically visible Actinic Keratosis lesions identified at the baseline visit and no new Actinic Keratosis lesions in the selected treatment area at Visit 4/Day 57.

2.2 Safety

Safety of the test and reference products will be compared by evaluating the nature, severity and frequency of their adverse event profiles. All adverse events that occur during the study (from the moment a subject signs an informed consent/assent) will be recorded. Descriptions of reactions or complaints will include the approximate date of onset, the date the adverse event ended, the severity of the adverse event, and the outcome. Comparisons between the treatment groups will be made by tabulating the frequency of subjects with one or more adverse events (classified into MedDRA terms) during the study. Pearson's Chi-Square test or Fisher's Exact test, whichever is most appropriate, will be used to compare the proportion of subjects in the two active treatment groups with any adverse event. [REDACTED]

Protocol No: PRG-NY-15-002

of the subject's adverse events (AEs). At this visit, the Follow-Up Telephone Call/Day15, Visit 3/Day 29 and Visit 4/Day 57 will be scheduled.

A Follow-Up Telephone Call will be made by study staff to the subject at Day 15 to review and assess subject compliance (diary completion), record AEs, update concomitant medication use, and to remind the subjects of the protocol requirements and next study visit schedule.

At Visit 3/Day 29 (Interim) and Visit 4/Day 57 (End of Study), subjects will be asked if they experienced any adverse events, taken any concomitant medications and generally complied with protocol requirements. The diary dispensed at Visit 2 will be collected and reviewed with the subject, and a new diary will be dispensed at Visit 3/Day 29. The diary dispensed at Visit 3 will be collected and reviewed at Visit 4/Day 57. Safety will be assessed by the monitoring of all adverse events (AEs) and clinically significant changes from Visit 1/Day 1 (Baseline) and an application site reaction assessment will be conducted at Visit 3/Day 29 and Visit 4/Day 57.

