5.10 Application Site Reaction Assessment

To the greatest extent possible, the same investigator who made Visit 1/Day 1 (Baseline) assessments will assess the application site reactions, grade them according to a 5-point scale and a designated staff will record them in the source document and eCRFs at each subsequent visit. This assessment must be conducted by qualified individuals listed on the Form FDA 1572 who have been delegated this task by the PI. [REDACTED]

At baseline (prior to initial dosing) and each subsequent visit, application site reactions of erythema, flaking/scaling, crusting, swelling, vesiculation/pustulation, and erosion/ulceration are to be recorded in the source document and eCRFs.

Application site reactions (erythema, flaking/scaling, crusting, swelling, vesiculation/pustulation, and erosion/ulceration) are not to be recorded as adverse events unless they result in either:

- The temporary discontinuation of the study medication.
- The discontinuation of the subject from the study.
- The use of a new concomitant medication in order to treat this event.

Any other application site reaction not listed above (such as pain, pruritus and infection) should be recorded as adverse events in the source document and eCRFs.

The following scale will be used for the Application Site Reaction Assessment:

Site Reaction	Description
Erythema	[REDACTED]
Flaking/scaling	[REDACTED]
Crusting	[REDACTED]
Swelling	[REDACTED]
Erosion/ulceration	[REDACTED]
Vesiculation/Pustulation	[REDACTED]

Site Reaction	Grading Criteria				
	0	I	I	I	I
██████████	██████████	██████████	██████████	██████████	██████████
██████████ ██████████	██████████	██████████ ██████████	██████████	██████████	██████████ ██████████
██████████	██████████	██████████	██████████	██████████	██████████ ██████████
██████████	██████████	██████████ ██████████	██████████ ██████████ ██████████	██████████ ██████████	██████████ ██████████ ██████████
██████████ ██████████	██████████	██████████ ██████████	██████████ ██████████ ██████████	██████████	██████████ ██████████
██████████ ██████████	██████████	██████████	██████████ ██████████ ██████████	██████████ ██████████ ██████████	██████████ ██████████ ██████████ ██████████

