Diaries will be dispensed for each enrolled subject. The subjects will be instructed to complete their diary after applying the subsequent dose of study medication. At Visit 2/Day 3, the study personnel will review the diary to determine subject dosing compliance, confirm use of any prohibited medications, assess AEs and a new diary will be dispensed to all subjects. At each subsequent visit, study personnel will review the diary card to determine if the subject used any prohibited medications, assess AEs and dispense a new diary (a diary will not be dispensed at Visit 4/ Day 57). In addition, each study subject will be reminded to return the previously dispensed tube (regardless of content) at Visit 2/Day 3 and the completed diary at the next visit. Study personnel will schedule the subject's next visit prior to the subject's departure.

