7. ADVERSE REACTIONS

The potential adverse reactions of generic Ingenol Mebubate Topical Gel 0.05% are anticipated to be similar to those observed in Picato[®] Topical Gel (Ingenol Mebutate Topical Gel 0.05%). The most common adverse reactions related to treatment with Picato[®] Topical Gel include local skin reactions, application site pain, application site pruritus, application site irritation, and nasopharyngitis. Eye disorders, including severe eye pain, eyelid edema, eyelid ptosis, and periorbital edema can occur after exposure. Severe local skin reactions such as vesiculation/pustulation, erosion/ulceration can occur.

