To compare the safety and efficacy profiles of Perrigo New York, Inc.'s Ingenol Mebutate Topical Gel 0.05% to Picato® Topical Gel 0.05% (Ingenol Mebutate Topical Gel 0.05%) and to demonstrate the superior efficacy of the two active formulations over that of the vehicle in the treatment of Actinic Keratosis.

3 Study Design

For the purpose of exploring the above objectives, the study will be conducted as a double-blind, randomized, parallel-group, vehicle-controlled, multicenter trial.

Each subject will be randomly assigned to one of following treatment groups :

- (1) Test: Ingenol Mebutate Topical Gel 0.05%, Perrigo New York, Inc.
- (2) Reference: Picato® Topical Gel 0.05% (Ingenol Mebutate Topical Gel 0.05%), Leo Pharma Inc.
- (3) Vehicle of test product, Perrigo New York, Inc.

Subjects will be admitted into the study only after written informed consent has been obtained and all of the inclusion and none of the exclusion criteria have been met. Randomization will be performed according to a computer generated randomization scheme where the treatment group designation has been assigned to the subject number. The treatment designation will remain blinded until the final database is closed. An independent third party will generate and hold the randomization code throughout the study. Randomized subjects will apply assigned

topical gel [redacted] once daily for two (2) consecutive days to the selected treatment area (one contiguous skin area of approximately 25cm² treatment area on the trunk/extremities) avoiding contact with the eyes, mouth and other body areas during and after gel application.

Subjects will be scheduled for an office visit for Visit 1/Day 1 (Baseline), Visit 2/Day 3 (±1 days) (Post-Treatment Interim), Visit 3/Day 29 (±3 days) (Interim), and Visit 4/Day 57 (±2 days) (End of Study). Safety will be assessed by monitoring adverse events at each visit and during a Follow-Up Phone Call/Day 15 (±3 days).

4 Populations To Be Analyzed

Three subject populations are defined as follows:

- (1) An intent-to-treat (ITT) subject is any individual who: (a) was randomized into the study, and (b) received and applied at least one dose of study medication;
- (2) A modified intent-to-treat (mITT) subject is any individual who: (a) was randomized into the study, (b) met eligibility criteria, (c) received and applied at least one dose of study medication, and (d) had at least one post-baseline efficacy assessment;

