The severity of application site reactions such as erythema, flaking/scaling, crusting, swelling, vesiculation/pustulation, and erosion/ulceration will be summarized by treatment group and visit using frequencies and percentages of subjects.

Safety comparisons will be performed only for the ITT population.

6 Appendices

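### No application site reaction grading is scheduled on Days 5 to 25, and untreated reactions in that gap are not systematically captured, so the Test-Reference comparison describes only three post-dose visits

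*Protocol*

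**What the plan says.** **Grading.** Protocol 5.10 starts its recording rule with "At baseline (prior to initial dosing) and each subsequent visit, application site reactions of erythema" and goes on to name flaking/scaling, crusting, swelling, vesiculation/pustulation and erosion/ulceration. The visit description after Protocol 2.2 adds that "an application site reaction assessment will be conducted at Visit 3/Day 29 and Visit 4/Day 57". SAP section 3 gives the post-baseline visits as "Visit 2/Day 3 (±1 days) (Post-Treatment Interim), Visit 3/Day 29 (±3 days) (Interim), and Visit 4/Day 57 (±2 days) (End of Study"). Protocol 5.11 and 5.16 limit dosing to Days 1 and 2.

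**Contact between Visits 2 and 3.** The only planned contact is a Day 15 telephone call, made "to review and assess subject compliance (diary completion), record AEs, update concomitant medication use" and to give reminders. Protocol 5.11 describes the diary review at later visits: "study personnel will review the diary card to determine if the subject used any prohibited medications, assess AEs and dispense a new diary".

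**Adverse event rule.** Under Protocol 5.10 the six reactions "are not to be recorded as adverse events unless they result in either" a temporary stop of study medication, discontinuation from the study, or a new concomitant medication to treat them. Other local reactions, such as pain, pruritus and infection, are recorded as adverse events.

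**Analysis.** SAP 5.6 says that reaction severity "will be summarized by treatment group and visit using frequencies and percentages of subjects". Protocol 8.1.5 plans a descriptive Test-Reference comparison of the frequency and distribution of the six reactions.

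**Expected reactions.** Protocol section 7 puts local skin reactions first among the common reactions and warns: "Severe local skin reactions such as vesiculation/pustulation, erosion/ulceration can occur".

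**The concern.** Comparing the safety of Test and Reference is a stated objective, and local reactions are the most prominent risk that the protocol names. Three rules act together: no grading is scheduled for about three weeks soon after dosing, the call in that period has no described reaction check, and the adverse event route is closed to reactions that need no new drug and do not end participation. A subject with untreated erosion that appears after Visit 2 and heals before Visit 3 could contribute nothing to either the reaction tables or the adverse event tables. Untreated pruritus in the same subject over the same days would be recorded. At stake is whether the reaction tables can support a statement about how often, and how severely, subjects reacted in each arm.

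**Working it through.** The plan states no figure on this point, so there is none to reproduce. The check is day arithmetic, followed by a trace of where a reaction in the gap would be recorded.

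**Inputs.** Visit 2 is Day 3 ±1 (Days 2-4), Visit 3 is Day 29 ±3 (Days 26-32) and Visit 4 is Day 57 ±2 (Days 55-59), from SAP section 3. The call is Day 15 ±3 (Days 12-18), from Protocol 5.12.3.

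**Interval between Visits 2 and 3.**
- Nominal: 29 − 3 = 26 days.
- Shortest: 26 − 4 = 22 days.
- Longest: 32 − 2 = 30 days.
- Days outside every scheduled grading window for every subject: 4 + 1 = Day 5 to 26 − 1 = Day 25.

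The protocol's table of contents gives the Visit 2 window as +1 day only. The longest interval is then 32 − 3 = 29 days, and Days 5 to 25 are unchanged. The two statements of the window should be reconciled.

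**Where a reaction in the gap would appear in the visible text.**

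| Reaction | Reaction table | Adverse event record |
|---|---|---|
| Still present at Visit 2 or Visit 3 | Yes, at that day's grade; the peak may be missed | Only if an exception applies |
| Treated with a new medication, or ends participation | Only if graded at a visit | Yes |
| Seen at an unscheduled visit | Can be graded, but the visit is discretionary | Only if an exception applies |
| Untreated, rises and heals between Visits 2 and 3, no extra visit | No | No |

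The temporary-stop exception has little force in the gap, because no dose remains after Day 2. The last row is the gap. The application site paragraph of SAP 5.6 tabulates by visit and gives no worst post-baseline summary.

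**Effect on the comparison.** The documents give no time course, so the following is illustration only. Assume true rates of a severe worst grade of 30% (Test) and 20% (Reference), a difference of 10 points, and let s be the share of those subjects whose severe grade is missed in the gap. Recorded rate = true rate × (1 − s).

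| s Test | s Reference | Recorded Test | Recorded Reference | Difference |
|---|---|---|---|---|
| 25% | 25% | 22.5% | 15% | 7.5 points |
| 50% | 50% | 15% | 10% | 5 points |
| 75% | 75% | 7.5% | 5% | 2.5 points |
| 25% | 75% | 22.5% | 5% | 17.5 points |
| 75% | 25% | 7.5% | 15% | −7.5 points |

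With equal missed shares the absolute difference shrinks, while the ratio stays at 1.5. With unequal shares the difference can widen or change sign.

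**The case against.** A reader might infer that these reactions are barred from adverse event recording and never captured, that severe ones go unrecorded, and that the plan therefore makes the products look alike. The documents do not support that reading.

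- **Exceptions exist.** A reaction that needs a new medication or ends participation is an adverse event, and the Day 15 call and Visit 3 both collect adverse events and concomitant medication. Protocol 7.2 describes severe events as ones that traditionally need treatment, so many severe reactions would meet an exception. Serious events are reportable in any case (7.4), and Protocol 5.12.6 permits an unscheduled visit at any time.
- **Timing is unknown.** Nothing visible shows that reactions peak or heal between Visits 2 and 3. If most peak by Visit 2 or persist to Visit 3, little is lost.
- **Direction is unknown.** Shrinkage toward zero requires similar missed shares in the two arms.
- **Redaction.** The visit and call procedures (5.12), the schedule (5.13 and SAP 6.2) and parts of 5.10 are blacked out, so a further capture step cannot be excluded.
- **Limited role.** The reaction comparison is descriptive, with no test or margin. The safety comparison that is tested concerns any adverse event, and the efficacy conclusions are untouched.

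All of this stands, and it limits the point to untreated reactions that do not end participation, with an unknown extent. It does not close the gap: unscheduled visits are discretionary, and no visible rule gives such a reaction a place to be recorded.

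**Conclusion.** The point holds as a cheap improvement to the descriptive safety data. In the visible text, no grading of the six reactions is scheduled on Days 5 to 25, and Visits 2 and 3 are 22 to 30 days apart. Untreated reactions that arise, peak or resolve in between are not systematically captured unless an unscheduled visit occurs. The by-visit tables therefore give prevalence on three post-dose days, and should not be read as incidence or worst severity over follow-up.

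The day count rests only on the stated visits and windows. The number of reactions missed cannot be estimated from the documents, and no direction of bias should be claimed. The conclusion also assumes that the redacted procedures contain no between-visit reaction check. If they do, only the missing worst-grade summary in SAP 5.6 remains.

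**What to change.** Use the contacts already planned.

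1. Add the six reactions to the diary dispensed at Visit 2: presence, start and stop dates, and worst severity in lay terms.
2. Ask about the same six reactions at the Day 15 call and at Visit 3. Put these questions after the non-specific adverse event question of Protocol 7.3 and record the answers on a separate form, so that prompting does not alter how adverse events are elicited. The adverse event rule in 5.10 need not change.
3. In SAP 5.6 add a table by arm of the worst post-baseline investigator grade for each reaction, with the Test-Reference difference. Add a separate table of subject-reported reactions between visits, and do not pool the two sources, since 5.10 reserves grading for qualified, delegated individuals.

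**Cost.** Edits to the diary, call script and eCRF, and two SAP tables; no extra visit. The between-visit data are subject-reported, less precise than the 5-point investigator scale and subject to recall. Using the call splits the nominal 26-day recall period into 15 − 3 = 12 days and 29 − 15 = 14 days, and the diary reduces reliance on memory further. If the diary and call can no longer be changed, the worst-investigator-grade table can still be added, with a note that it covers only the days on which reactions were graded.

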3.2 Study Population

Healthy male and female subjects, at least 18 years of age, with 4 to 8 clinically typical, visible, discrete Actinic Keratosis lesions within a contiguous 25cm² treatment area on either the trunk or extremities who meet all eligibility criteria will be enrolled in this multicenter study.

4. SELECTION AND WITHDRAWAL OF STUDY SUBJECTS

4.1 Inclusion Criteria

Subjects **must** meet all of the following criteria:

1. Subject must sign an Institutional Review Board (IRB) approved written informed consent/assent for this study. Subjects under the legal age of consent for their respective state must sign an IRB approved written informed consent/assent in addition to a parent or legally authorized representative.
2. Subjects must be healthy males or females, at least 18 years of age.
3. Subjects must be in general good health and free from any clinically significant disease, other than Actinic Keratosis that might interfere with the treatment assessment of Actinic Keratosis or study evaluations.
4. Subjects must have a clinical diagnosis of Actinic Keratosis, defined as having 4 to 8 clinically typical, visible and discrete, non-hyperkeratotic, non-hypertrophic, Actinic Keratosis lesions within a contiguous 25cm² treatment area on either the trunk or extremities (i.e. to be designated as the treatment area).

5. [REDACTED]
[REDACTED]
[REDACTED]
[REDACTED]
[REDACTED].

[REDACTED]

6. [REDACTED]

7. Subjects must be willing and able to understand and comply with the requirements of the study, apply the study medication as instructed, refrain from use of all other topical Actinic Keratosis medication during the 57 day (8 week) study period, return for the required study visits, comply with therapy prohibitions, and are able to complete the study.

8. [REDACTED]

4.2 Exclusion Criteria

Subjects may **not** be enrolled if any of the following criteria exist:

1. Subjects who are pregnant, nursing, or planning a pregnancy within the study period.
2. Subjects who are immunocompromised or HIV positive or who have any immune-system disorders including auto-immune diseases.
3. Subjects who have or had an active herpes infection [REDACTED] prior to the Visit1/Day 1 (Baseline) (i.e., including presence of herpes labialis).
4. Subjects who have any evidence of systemic cancer, squamous cell carcinoma, basal cell carcinoma, or any other cancer in the treatment area.

5. [REDACTED]
[REDACTED].

6. Presence of any confounding skin conditions in the treatment area that may be made worse by treatment with Ingenol Mebutate gel 0.05% [REDACTED]

7. [REDACTED]
[REDACTED]
[REDACTED]

[REDACTED]
[REDACTED]

[REDACTED]
[REDACTED]
[REDACTED]
[REDACTED]

[REDACTED]
[REDACTED]
[REDACTED]

- [REDACTED]
- [REDACTED]
- [REDACTED]
- [REDACTED]
- [REDACTED]
- [REDACTED]

11. Subjects who have had or are scheduling elective surgery within 1 month (30 days) before or after the study period.

12. Use [REDACTED] prior to Visit 1/Day 1 (Baseline) or planned use during the study of:

- [REDACTED]
- [REDACTED]
- [REDACTED]
- [REDACTED]
- [REDACTED]
- [REDACTED],

[REDACTED]

- [REDACTED]
13. Subjects who are undergoing treatment or received treatment with the following [REDACTED] [REDACTED] of Visit 1/Day 1 (Baseline) and [REDACTED] of the selected treatment area or planned anytime during the study.
 - [REDACTED]
 - [REDACTED]
 - [REDACTED]
 - [REDACTED]
 14. Use of Ingenol Mebutate gel 0.05% [REDACTED] of Visit 1/Day 1. Previous use [REDACTED] of Ingenol Mebutate gel 0.05% is allowed if a different treatment area was successfully treated.)
 15. History of unresponsiveness, hypersensitivity or allergy to ingenol mebutate therapy and/or any ingredient in the study medication.
 16. Subjects who used PUVA (psoralen plus ultraviolet A therapy), or UVB therapy in the treatment area [REDACTED] prior to Visit 1/Day 1 (Baseline) or are planning to receive treatment with PUVA therapy, UVB therapy, nonprescription UV light sources anywhere on the body during the study.
 17. Subjects who have taken systemic chemotherapy medications [REDACTED] prior to Visit 1/Day 1 (Baseline) or planned use anytime during the study.
 18. [REDACTED]
 19. [REDACTED]
 20. [REDACTED]
 21. Start [REDACTED] of dose of hormonal treatment (oral, implanted, topical contraceptives and androgens) [REDACTED] or planned start or change throughout the study. Use of such therapy must remain constant during the study.
 22. Subject consumes excessive alcohol, abuses drugs, or has a condition that could compromise the subject's ability to comply with study requirements.
 23. Participation in any clinical study involving an investigational product, agent or device (that might influence the intended effects or mask the side effects of study medication) in the 30 days prior to Visit 1/Day 1 (Baseline) or throughout the study.
 24. Previous enrollment in this study or current enrollment in this study at another participating site.

- 25. Employee (or employee’s family member) of the research center or private practice, or subjects who have a conflict of interest.
- 26. Subjects who in the opinion of the investigator, are unlikely to be able to follow the restrictions of the protocol and complete the study.

4.3 Medications, Supplements, Other Substances and Procedures Prohibited Before Enrollment and During the Study

The medications prohibited prior to enrollment, and required washout period, are listed in Table 4.3.1 with the subject exclusion criteria.

Table 4.3.1 Medications, Supplements, and Other Substances Prohibited for Study Entry

Prohibited Medications, Supplements, and Other Treatment	Exclusion Criteria Number	Washout Period Prior to Randomization
[REDACTED]	1	[REDACTED]
[REDACTED]	2	[REDACTED]
[REDACTED]	2	[REDACTED]
[REDACTED]	[REDACTED]	[REDACTED]
[REDACTED]	2	[REDACTED]
[REDACTED]	2	[REDACTED]
[REDACTED]	2	[REDACTED]

[REDACTED]
 
[REDACTED]
 
[REDACTED]
	
[REDACTED]
	
[REDACTED]

---	-------------------	-------------------

Subjects must not take the treatments listed in TABLE 4.3.2 during study participation.

Table 4.3.2 Medications (Prescription and Over-the-Counter), Supplements, and Other Treatments Prohibited During the Study

Prohibited Medications, Over-The-counter (OTC) medications, and Treatments	Location	Exclusion Period Restrictions

[REDACTED]
 
[REDACTED]
 
[REDACTED]
	
[REDACTED]
 
[REDACTED]
 
[REDACTED]
	
[REDACTED]
 
[REDACTED]

[REDACTED]
 
[REDACTED]
 
[REDACTED]
 
[REDACTED]
 
[REDACTED]
	
[REDACTED]
	
[REDACTED]
 
[REDACTED]
 
[REDACTED]
 
[REDACTED]


[REDACTED]
 
[REDACTED]
 
[REDACTED]
	
[REDACTED]
 
[REDACTED]
 
[REDACTED]
	
[REDACTED]
 
[REDACTED]

[REDACTED]
 
[REDACTED]
 
[REDACTED]
 
[REDACTED]
 
[REDACTED]
 
[REDACTED]
 
[REDACTED]
 
[REDACTED]
 
[REDACTED]
	
[REDACTED]
	
[REDACTED]
 
[REDACTED]

[REDACTED]
 
[REDACTED]
 
[REDACTED]
 
[REDACTED]
 
[REDACTED]
	
[REDACTED]
 
[REDACTED]
 
[REDACTED]
	
[REDACTED]

[REDACTED]
	
[REDACTED]
	
[REDACTED]

[REDACTED]

[REDACTED]	[REDACTED]	
[REDACTED]	[REDACTED]	[REDACTED]

[REDACTED]

